2.3.3 Anti-alirocumab antibody population

The anti-alirocumab antibody analysis will be performed on all randomized and treated patients (safety population) with an available ADA sample at Week 0 (baseline) and at least 1 available ADA sample post first double-blind IMP injection and up to follow-up visit for patients not proceeding into OLTP, up to first open-label IMP injection for patients proceeding into OLTP.

2.3.4 Pharmacokinetics population

The PK analysis will be performed on all randomized and treated patients (safety population) with at least one evaluable PK sample post the first double-blind IMP injection.

2.3.5 Open-label treatment population

The open-label treatment population considered for all analyses in the open-label treatment period will be all randomized patients who received at least one dose or part of dose of open-label IMP.

2.3.6 Alirocumab safety population

The alirocumab safety population considered for the safety analyses combining exposure of alirocumab during DBTP and OLTP will be the randomized patients who actually received at least one dose or partial dose of alirocumab IMP (double-blind or open-label).

2.4 STATISTICAL METHODS

2.4.1 Demographics and baseline characteristics

Parameters described in [Section 2.1.1](#) will be summarized by treatment group and overall using descriptive statistics.

Continuous data will be summarized using the number of available data, mean, standard deviation (SD), median, minimum, and maximum for each treatment group. First quartile (Q1)

and third quartile (Q3) will be also provided for baseline lipid parameters, HbA1c and eGFR. Categorical and ordinal data will be summarized using the number and percentage of patients in each treatment group.

Parameters will be summarized on the randomized population analyzed in the as-randomized treatment group. Similar analyses will be done on the ITT population, safety population, OLT population, and alirocumab safety population

The reason why statin is not appropriate or why statin dose cannot be increased from the lowest strength for the patients will be descriptively summarized using the number and percentage of patients by each treatment group. The reason specified in eCRF will be listed for the patient with “other reason”.

2.4.2 Prior, concomitant, or post-treatment medications

The prior, concomitant and post-treatment medications will be presented during DBTP for the safety population.

Medications will be summarized by treatment group according to the WHO-DD dictionary, considering the first digit of the anatomical therapeutic chemical (ATC) class (anatomic category) and the first 3 digits of the ATC class (therapeutic category). All ATC codes corresponding to a medication will be summarized, and patients will be counted once in each ATC category (anatomic or therapeutic) linked to the medication. Therefore patients may be counted in several categories for the same medication.

The table for prior medications will be sorted by decreasing frequency of ATC followed by all other therapeutic classes based on the overall incidence across treatment groups. In case of equal frequency across anatomic or therapeutic categories, alphabetical order will be used.

The tables for concomitant and post-treatment medications will be sorted by decreasing frequency of ATC followed by therapeutic class based on the incidence in the Alirocumab 150mg Q4W group. In case of equal frequency across anatomic or therapeutic categories, alphabetical order will be used.

All concomitant and post-treatment medications recorded during the OLTP will be summarized in the OLT population.

2.4.3 Extent of investigational medicinal product exposure and compliance

The extent of IMP exposure and compliance will be assessed and summarized for the safety population (using as-treated treatment group), OLT population and alirocumab safety population (for first step analysis only).

2.4.3.1 Extent of investigational medicinal product exposure

Injection (alirocumab or placebo)

Double-blind IMP injections are those administered from randomization to completion or discontinuation of the double-blind study treatment. These injections contain:

- placebo Q2W for patients randomized in the Placebo Q2W group,
- placebo Q4W (to maintain the blind) or 150 mg Q4W of alirocumab for patients randomized in the Alirocumab 150 mg Q4W group.

- 150 mg Q2W of alirocumab for patients randomized in the Alirocumab 150 mg Q2W group.

The total exposure during the DBTP will be assessed using descriptive statistics for:

- Duration of double-blind IMP injection exposure in weeks defined as: (date of last dose of double-blind IMP injection +14 – date of first dose of double-blind IMP injection) / 7, regardless of intermittent discontinuations (see [Section 2.5.3](#) for calculation in case of missing or incomplete data). Non-integer values will be rounded to 1 decimal place;
- The total number of double-blind IMP injections by patient.

Duration of double-blind IMP injection exposure will be summarized using number, mean, SD, median, minimum and maximum. In addition, it will be summarized according to the following categories: ≥ 1 day and < 4 weeks, ≥ 4 weeks and < 8 weeks, ≥ 8 weeks and < 10 weeks, ≥ 10 weeks.

The total exposure during the OLTP will be assessed using descriptive statistics for:

- Duration of open-label IMP injection exposure in weeks defined as: (date of last dose of open-label IMP injection +14 – date of first dose of open-label IMP injection) / 7, regardless of intermittent discontinuations (see [Section 2.5.3](#) for calculation in case of missing or incomplete data). Non-integer values will be rounded to one decimal place;
- The total number of open-label IMP injections by patient.

Duration of open-label IMP injection exposure will be summarized using number, mean, SD, median, minimum and maximum. In addition, it will be summarized according to the following categories: ≥ 1 day and < 12 weeks, ≥ 12 weeks and < 24 weeks, ≥ 24 weeks and < 36 weeks, ≥ 36 weeks and < 48 weeks, ≥ 48 weeks.

The total exposure during alirocumab exposed period (defined in [Section 2.4.5](#)) for first step analysis only will be assessed using descriptive statistics for:

- Duration of alirocumab IMP injection exposure in weeks defined as:
 - For Alirocumab 150 mg Q4W group and Alirocumab 150 mg Q2W group: (date of last dose of IMP injection (double-blind or open-label) +14 – date of first dose of double-blind IMP injection) / 7, regardless of intermittent discontinuations (see [Section 2.5.3](#) for calculation in case of missing or incomplete data). Non-integer values will be rounded to one decimal place;
 - For Placebo Q2W group: (date of last dose of open-label IMP injection +14 – date of first dose of open-label IMP injection) / 7, regardless of intermittent discontinuations (see [Section 2.5.3](#) for calculation in case of missing or incomplete data). Non-integer values will be rounded to one decimal place;
- The total number of alirocumab IMP injections by patient.

Duration of alirocumab IMP injection exposure will be summarized using number, mean, SD, median, minimum and maximum. In addition, it will be summarized according to the following

categories: ≥ 1 day and <12 weeks, ≥ 12 weeks and <24 weeks, ≥ 24 weeks and <36 weeks, ≥ 36 weeks and <48 weeks, ≥ 48 weeks and <60 weeks, ≥ 60 weeks.

Titration

For the OLTP, the number and percentage of patients with an up-titration at Week 24 will be described. Patients with an up-titration are defined as up-titrated patients according to IRT Week 24 transaction with at least 1 injection of alirocumab 150 mg Q2W afterwards.

2.4.3.2 Compliance

Compliance for the DBTP will be assessed using the following parameters:

- The mean injection frequency of IMP double-blind injections will be defined for each patient as the average number of days between 2 consecutive double-blind injections, that is: (last double-blind injection date – first double-blind injection date)/(number of double-blind injections -1) for patients receiving at least 2 injections.
- The overall compliance for double-blind injections will be defined for each patient as: 100- (%days with under-planned dosing + %days with above-planned dosing). Under-planned and above-planned dosing will be defined as follows, considering that injections should be performed every 2 weeks (± 3 days as per protocol):
 - The % days with under-planned dosing will be defined for each patient as the number of days with no injection administered within the previous 17 days divided by the duration of IMP injection exposure in days. For example if a patient takes a dose 18 days after his/her previous injection, then 1 day is counted as a day under-planned dosing.
 - The % days with above-planned dosing will be defined for each patient as the number of days with more than one injection administered within the 11 days before divided by the duration of IMP injection exposure in days. For example if a patient takes a dose 9 days after his/her previous injection, then 2 days are counted as days above-planned dosing.

For the OLTP, only mean injection frequency will be assessed for compliance.

- The mean injection frequency of IMP open-label injections will be defined for each patient as the average number of days between 2 consecutive open-label injections, that is: (last open-label injection date – first open-label injection date)/(number of open-label injections -1) for patients receiving at least 2 injections.

These parameters will be summarized descriptively (N, Mean, SD, Median, Minimum and Maximum).

The percentage of patients whose overall compliance for injections is $<80\%$ will be also summarized as well as numbers and percentages of patients with 0%, $>0\%$ and $\leq 5\%$, $>5\%$ and $\leq 10\%$, $>10\%$ and $\leq 20\%$, and $>20\%$ days with above-planned dosing and numbers and percentages of patients with 0%, $>0\%$ and $\leq 5\%$, $>5\%$ and $\leq 10\%$, $>10\%$ and $\leq 20\%$, and $>20\%$ days with under-planned dosing.

According to protocol, cases of overdose are reported in the AE e-CRF pages and will be described in the AE analysis (see [Section 2.1.4.1](#)).

The mean injection frequency of IMP open-label injections (until and after Week 24 separately) will be summarized according to the up-titration status.

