When IMP injection is delayed more than 7 days from the scheduled injection time, or is completely missed, the patient should return to the original schedule of the IMP administration without administering the delayed injection. If the delay is less than or equal to 7 days from the missed date, the patient should administer the delayed injection and then resume the original dosing schedule of the IMP administration. At least 7 days must be needed between the IMP injections.

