10.1.3.2 Visit 5 / Week 2 (Day 15 ± 7)

Note: No blood sampling is scheduled.

- On-site visit
- IVRS/IWRS contact for allocation of a treatment kit according to the randomization list.
- IMP administration and compliance check, and 30 minutes observation after the IMP administration.
- Record concomitant medication.
- Measure vital signs including HR and BP.
- Collect AEs/SAEs information.
- Reminders:
 - An appointment will be given for the next study site visit (Week 4).
 - Remind patient to be in fasting conditions (i.e., overnight, at least 10 to 12 hours fast and refrain from smoking) for next study site visit. Also alcohol consumption within 48 hours and intense physical exercise within 24 hours preceding the next study site visit are discouraged.

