10.1.3.5 Visits 8 / Week 8 (Day 57 ± 7)

Note: Blood sample should be collected before IMP administration.

- On-site visit
- IVRS/IWRS contact for allocation of a treatment kit according to the randomization list.
- IMP administration and compliance check, and 30 minutes observation after the IMP administration.

- Record concomitant medication.
- Measure vital signs including HR and BP.
- Collect AEs / SAEs information.
- Obtain fasting blood sample for:
 - Lipids: total-C, measured and/or calculated LDL-C, HDL-C, TG, non-HDL-C, Apo-B, Apo A-1, Apo-B / Apo A-1ratio, and Lp(a).
 - Liver panel (ALT, AST, ALP, and total bilirubin).
- Serum alirocumab concentration (PK).
- Reminders:
 - An appointment will be given for the next study site visit (Week 10).
 - Remind patient to be fasting conditions (i.e., overnight, at least 10 to 12 hours fast and refrain from smoking) for next study site visit. Also alcohol consumption within 48 hours and intense physical exercise within 24 hours preceding the next study site visit are discouraged.

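### The SAP's double-blind compliance score uses a ±3-day tolerance credited to the protocol, whose windows are ±7 days at Weeks 2 to 8, so permitted timing is counted as off-plan days

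*SAP*

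**What the plan says.** SAP 2.4.3.2 defines overall double-blind compliance as 100 minus the percentages of under-planned and above-planned days, "considering that injections should be performed every 2 weeks (± 3 days as per protocol". Under-planned days are the "number of days with no injection administered within the previous 17 days". Above-planned days are the "number of days with more than one injection administered within the 11 days before". Both are divided by the exposure duration in days, which SAP 2.4.3.1 builds as "date of last dose of double-blind IMP injection +14 – date of first dose of double-blind IMP injection) / 7" when expressed in weeks. The only patient-level cut-off on the overall score is 80%: "The percentage of patients whose overall compliance for injections is" below that value is tabulated, together with bands of under- and above-planned days.

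Protocol 8.1.2 has all double-blind injections given at the study site, so the visit windows govern them. Those windows are ±7 days at Weeks 2, 4, 6 and 8 (for example "Visit 5 / Week 2 (Day 15 ± 7" and "Visits 8 / Week 8 (Day 57 ± 7", each days), and ±3 days at Week 10 (10.1.3.6). The opening of Protocol section 10 and the flow chart in 1.2 agree. Protocol 8.1.2 adds: "If the delay is less than or equal to 7 days from the missed date, the patient should administer the delayed injection" and then return to the original schedule, with at least 7 days between injections. The protocol's own compliance section (11.4.1.2) uses only the mean interval between injections and has no tolerance.

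**The concern.** The SAP names the protocol as the source of its tolerance, but the tolerance matches the protocol for only one of the five double-blind injections after Day 1. SAP 1.5 and 1.6 declare no statistical modifications, so nothing marks this as a deliberate departure. A patient who takes a late injection as Protocol 8.1.2 directs, then resumes the schedule, is charged twice: once for the long gap before the injection and once for the short gap after it.

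At stake is what the compliance tables mean. They will be read as adherence to the protocol's schedule over the 12 weeks that support the primary endpoint. As defined, they mix missed injections with injections given when the protocol allowed.

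**Working it through.** **Inputs.** Planned injection days are 1, 15, 29, 43, 57 and 71 (Protocol 10.1.3). The windows are ±7 days for the second to fifth injections and ±3 for the sixth. The minimum gap is 7 days (Protocol 8.1.2). The SAP limits are 17 = 14 + 3 and 11 = 14 − 3 days.

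**Formula.** For each gap g between consecutive injections, under-planned days are max(0, g − 17) and above-planned days are max(0, 11 − g). Let U and A be their sums and D = last day − first day + 14. Compliance = 100 − 100 × (U + A)/D.

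**The SAP's own examples.** An 18-day gap gives 18 − 17 = 1 under-planned day. A 9-day gap gives 11 − 9 = 2 above-planned days. Both match the SAP. A perfect schedule has D = 71 − 1 + 14 = 84 and scores 100%.

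**Schedules inside the visit windows, scored by the SAP rule.**

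| Shift from plan | Gaps (days) | U + A | D | Compliance |
|---|---|---|---|---|
| Week 2, 4 days late | 18, 10, 14, 14, 14 | 1 + 1 = 2 | 84 | 97.6% |
| Week 2, 7 days late | 21, 7, 14, 14, 14 | 4 + 4 = 8 | 84 | 90.5% |
| Weeks 2 and 6, each 7 days late | 21, 7, 21, 7, 14 | 8 + 8 = 16 | 84 | 81.0% |
| Weeks 2 and 6, each 7 days early; Week 10, 3 days early | 7, 21, 7, 21, 11 | 8 + 8 = 16 | 81 | 80.2% |
| Week 2, 7 days early; Week 4, 7 days late | 7, 28, 7, 14, 14 | 11 + 8 = 19 | 84 | 77.4% |

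**When does a score fall below 80%?** I enumerated every whole-day schedule inside the windows with gaps of at least 7 days: 212,353 schedules.

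- The lowest score is 65.5% (Days 1, 8, 36, 43, 50, 74; 18 + 12 = 30 off-plan days over 87).
- Every schedule below 80% has at least one pair of neighbouring visits shifted in opposite directions. Among the 42,791 schedules without such a pair, the lowest score is 80.2% and none is below 80%.
- With late shifts only, and Week 10 at most 3 days late, the lowest score is 81.0%.
- Protocol section 10 says that after a changed visit the next one should follow the original schedule. If that means no two consecutive visits may be off their planned day, 2,079 schedules remain; the lowest score is 80.2% and none is below 80%.

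One case lies outside the visit windows but inside the late-injection rule: Weeks 2, 6 and 10 each 7 days late. The gaps are 21, 7, 21, 7, 21, so 12 + 8 = 20 days over 91, or 78.0%. It exceeds the ±3-day window at Week 10.

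**How much is due to measuring gaps rather than dates?** Protocol windows apply to scheduled dates; the SAP limits apply to gaps. Even if every visit were within ±3 days of its date, gaps of 8 to 20 days can occur. Days 1, 12, 32, 40, 60, 68 give 6 + 6 = 12 off-plan days over 81, or 85.2%. Conversely, widening the limits to 7 and 21 days clears the single 7-day delay (100%), but the last row of the table still has 28 − 21 = 7 off-plan days over 84, or 91.7%. About 31% of the enumerated schedules would still score below 100%.

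**The case against.** The SAP states its 11- and 17-day limits openly, gives worked examples and applies them alike in all three arms. A 21-day gap on a 14-day plan is a real departure from the intended interval, and describing it is legitimate. The protocol's own measure, the mean injection interval, is kept alongside. All of that stands, and it is why the 11/17-day figures could be kept as a stricter description. It does not rescue the statement that the tolerance comes from the protocol.

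Three stronger readings are tempting, and the documents do not support them.

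- *Patients who follow the protocol will be reported as non-compliant.* The SAP has no such label. Its only cut-off on the overall score is 80%, and one full 7-day shift leaves a patient at 90.5%.
- *Most patients will be affected.* In the enumeration, 95.6% of schedules score below 100% and 2.4% below 80%. These are shares of calendar combinations, each weighted equally, so that a 7-day shift counts as much as an on-time visit. The documents give no basis for reading them as patient proportions. Part of the 95.6% also comes from scoring gaps instead of dates, not from the wrong tolerance.
- *The ITT and on-treatment results are compromised.* Neither uses this measure. The ITT estimand takes all values regardless of adherence. The mITT population depends on dosing, available LDL-C values and the 21 days after the last injection. The MMRM and the subgroup analyses have no compliance term. The open-label period uses mean injection frequency only.

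**Conclusion.** The point holds as a mismatch between the SAP and the protocol in a descriptive measure. The ±3-day attribution is wrong for four of the five double-blind injections after Day 1, and permitted timing lowers the reported score: to 90.5% for one 7-day delay and to 81.0% for two. Inside the visit windows, scores below 80% arise only if large opposite shifts at neighbouring visits are accepted as in-window (77.4% in the example). Whether they are accepted depends on how the section 10 instruction about the next visit is read. How often any of this will occur cannot be judged from the documents.

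The consequence is limited to the double-blind compliance tables. No efficacy or safety population, estimand or model changes. It is a minor point, worth correcting because those figures would not measure what the SAP says they measure.

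**What to change.** Reconcile SAP 2.4.3.2 with the protocol in one of two ways.

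1. Score each double-blind injection against its own scheduled date and protocol window, and count only missed or out-of-window injections as off-plan. This should be date-based; simply widening the gap limits does not remove the problem. The SAP should state how the Week 10 window and the 7-day late-injection rule are applied together.
2. Delete the reference to the protocol and present the 11/17-day figures as a stricter descriptive measure beside the window-based one.

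Neither option takes a position on which dosing window is right. The cost is SAP wording and one derivation. The inputs are injection dates, which the existing compliance formulas already use.

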2.4.4 Analyses of efficacy endpoints

For statistics where international and conventional units do not impact the results (e.g. means and least square (LS) means for percent changes from baseline, p-values for both percent and absolute changes from baseline, rates of patients below a threshold), derivations will be done and statistical models will be run using conventional units. For other statistics (e.g. descriptive statistics at baseline [REDACTED] derivations will be done with both international and conventional units.

Statistical analyses for the primary and secondary efficacy endpoints will be conducted in the DBTP. [REDACTED]

2.4.4.1 Analysis of primary efficacy endpoint(s)

2.4.4.1.1 Primary efficacy analysis

In the primary analysis, stratification factor of statin will be considered as covariate. Consistency of treatment effects between the randomization strata will be evaluated. In case there is heterogeneity of treatment effects at Week 24, particularly treatment group-by-stratification factor of statin interaction, then analysis by the strata will be performed as secondary.

The percent change from baseline in calculated LDL-C at Week 12 as defined in [Section 2.1.3.1](#) will be analyzed in the ITT population using a mixed-effect model with repeated measures (MMRM) approach. All post-baseline data available within Week 4 to Week 12 analysis windows will be used and missing data are accounted for by the MMRM model. The model will include the fixed categorical effects of treatment group (Placebo Q2W, Alirocumab 150 mg Q4W and Alirocumab 150 mg Q2W), stratification factor of statin (Yes/No) as per IRT, time point (Week 4, Week 8, Week 10, Week 12), treatment-by-time point interaction, and statin-by-time point interaction, as well as, the continuous fixed covariates of baseline LDL-C value and baseline value-by-time point interaction.

This model will be run using SAS Mixed procedure with an unstructured correlation matrix to model the within-patient errors. Parameters will be estimated using restricted maximum likelihood method with the Newton-Raphson algorithm. Denominator degrees of freedom will be estimated using Satterthwaite's approximation. This model will provide baseline adjusted least-squares means estimates at Week 12 for each treatment groups with their corresponding standard errors (SEs). To compare each alirocumab group to the Placebo Q2W group, an appropriate contrast statement will be used to test the differences of these estimates, at the 2-sided 0.025 level.

Within group least-squares means and standard errors will be provided, using weights equal to the observed proportion of patients in strata variable levels in the study population (i.e. “population weight”) rather than equal weights. Population weights are considered more appropriate than equal coefficients due to unbalances observed in the study population between levels of the randomization stratification factors.

Let μ_0 and μ_1 be the population means of the percent change from baseline in calculated LDL-C at Week 12 under Placebo Q2W group and each alirocumab group, respectively. The hypothesis that will be tested is “ $H_0: \mu_0 = \mu_1$ ” versus $H_1: \mu_0 \neq \mu_1$ ”.

Alirocumab group will be compared to placebo using an appropriate contrast tested at the two-sided 0.05 level, with corresponding least squares estimate of the mean difference between groups, SE and 97.5% CI.

In addition, the difference between the two alirocumab arms Q4W and Q2W will also be provided, with a 95% CI using an appropriate contrast from the same MMRM model.

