11.4.2.1 Analysis of primary efficacy endpoint(s)

See also [Section 9.1.1](#).

The primary efficacy endpoints, percentage change in calculated LDL-C from baseline to Week 12 will be analyzed in the ITT population using mixed-effect model with repeated measures (MMRM) approach. All post-baseline data available within Week 4, Week 8, Week 10, and Week 12 analysis windows will be used (on-treatment and off-treatment through Week 12) and missing data will be accounted for by the MMRM model.

The model will include the fixed categorical effects of treatment group (placebo, alirocumab 150 mg Q4W, and alirocumab 150 mg Q2W), time point (Week 4, Week 8, Week 10, and Week 12), stratification factor of statin (Yes/No), treatment-by-time point interaction and statin-by-time point interaction, as well as the continuous fixed covariates of baseline calculated LDL-C value, and baseline value-by-time point interaction.

This model will be run using SAS Mixed procedure with an unstructured correlation matrix to model the within-patient errors. Parameters will be estimated using restricted maximum likelihood method with the Newton-Raphson algorithm. Denominator degrees of freedom will be estimated using Satterthwaite's approximation. This model will provide baseline adjusted least-squares means (LS means) estimates at Week 12 for each treatment group with their corresponding standard errors (SEs). Let μ_0 and μ_1 be the population means of the percentage change from the baseline in calculated LDL-C at Week 12 under placebo and alirocumab, respectively. The

hypothesis that will be tested is “ $H_0: \mu_0 = \mu_1$ ” versus $H_1: \mu_0 \neq \mu_1$ ”. Each alirocumab arm will be compared to placebo group (at significance level of 2.5%) using appropriate contrasts, and the 97.5% confidence interval (CI) of the difference will be provided.

[REDACTED]

Subgroup analyses will be performed in order to assess the consistency of the treatment effect within stratification factor of statin (Yes/No).

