11.5 TIMING OF ANALYSES

The analysis will be conducted in two steps. In Japan, data up to 24 weeks are required for the drug application.

11.5.1 First step: Efficacy and safety analyses using data up to 24 weeks after randomization (including 12 weeks double-blind).

The first analysis will be conducted when all patients have been randomized and have at least all their data up to Week 24 (including 12 weeks DBTP and 12 weeks OLTP) collected and validated, and will consist in the final analysis of the primary and secondary efficacy endpoints up to Week 12 ([Section 9.1](#)).

The safety analysis will be performed on all safety data up to Week 24 collected and validated.

The results of the first analysis will not be used to change the conduct of the ongoing study in any aspect. Since primary and key secondary efficacy endpoints analysis up to Week 12 will have been analyzed concluded in all patients at the time of this first analysis, the significance level will be 0.025 for each comparison between the alirocumab group and placebo group.

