1.3 DETERMINATION OF SAMPLE SIZE

The study is expected to enroll approximately 159 patients.

Two pairwise comparisons will be performed (Alirocumab 150 mg Q4W versus Placebo Q2W and Alirocumab 150 mg Q2W vs. Placebo Q2W). In order to handle multiple comparisons Bonferroni adjustment will be used, i.e., the alpha level for each comparison is 0.025 to obtain an overall study alpha level of 0.05.

[figure not shown]
A sample size of 38 patients in the ITT population (19 in alirocumab group and 19 in placebo group) will have 90% power to detect a difference of 30% in mean percentage change in calculated LDL-C in any pairwise comparison with a 0.025 two-sided significance level and assuming a common standard deviation of 25%.

As a result, the total sample size needed for efficacy will be 57 patients (19 in each of the two alirocumab arms and 19 in the placebo arm).

The sample size is also considered in order to obtain long-term safety data. A sample size of 159 patients (randomization ratio 1: 1: 1, i.e., 53 in Alirocumab 150 mg Q4W, 53 in Alirocumab 150 mg Q2W, and 53 in Placebo Q2W) will allow having long-term open-label safety data. With this sample size, 100 patients are expected to be exposed to alirocumab for a minimum of 12 months providing that the proportion of drop out in the entire study duration (from randomization to Week 64) is 36%, which is obtained using exponential distribution with the same hazard as that of 30% dropout rate within 12 months. Moreover, with 100 patients treated with alirocumab for at least 12 months, AEs with a rate ≥ 0.03 will be detected with 95% probability.

Therefore, 159 patients (53 in Alirocumab 150 mg Q4W, 53 in Alirocumab 150 mg Q2W, and 53 in Placebo Q2W) will be needed to evaluate both efficacy and safety.

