2.4.4.2.6 Summary of results per time point

2.4.4.3 Multiplicity issues

The multiplicity appears in two kinds in this study, due to the presence of the 2 arms of alirocumab 150 mg Q4W and 150 mg Q2W that are compared with placebo, and due to the multiple key secondary efficacy endpoints.

The overall type I error will be controlled at 0.05 by performing each pairwise test (alirocumab 150 mg Q4W vs. placebo, and alirocumab 150 mg Q2W vs. placebo) for the main efficacy endpoint at the 0.025 level.

Then, a hierarchical procedure will be used for each pairwise comparison to control the type I error and to handle multiple endpoints. If the primary endpoint analysis is significant at the 2.5% alpha level, the key secondary efficacy endpoints will be tested sequentially at the 0.025 level, using the order defined in [Section 2.1.3.2.1](#). Hierarchical procedure for comparisons of alirocumab 150 mg Q4W versus placebo, and alirocumab 150 mg Q2W versus placebo will be processed separately.

No further adjustments will be made for other secondary endpoints for which p-values will be provided for descriptive purpose only (no claim).

In addition, no further adjustment will be made for multiple analyses (i.e., first and second analyses), since the primary efficacy endpoint and the key secondary efficacy endpoints will all have been conducted at the time of first analysis. [REDACTED]

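### SAP 2.4.4.1.1 sets two different significance levels for the same primary contrast, 0.025 and 0.05; the 0.05 contradicts the rest of the plan and should read 0.025

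*SAP*

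**What the plan says.** The primary analysis is an MMRM of percent change in calculated LDL-C, with each alirocumab arm contrasted with placebo at Week 12. SAP 2.4.4.1.1 states the test level twice:

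- On introducing the contrasts: "an appropriate contrast statement will be used to test the differences of these estimates, at the 2-sided 0.025 level".
- After the hypotheses: "Alirocumab group will be compared to placebo using an appropriate contrast tested at the two-sided 0.05 level", continuing "with corresponding least squares estimate of the mean difference between groups, SE and 97.5% CI".

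Elsewhere the per-comparison level is uniform:

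- SAP 1.3: "the alpha level for each comparison is 0.025 to obtain an overall study alpha level of 0.05". The sample size is built on that level.
- SAP 2.4.4.3: "The overall type I error will be controlled at 0.05 by performing each pairwise test" of the main endpoint at 0.025. The key secondary hierarchy opens on the condition "If the primary endpoint analysis is significant at the 2.5% alpha level".
- Protocol 11.1 and 11.4.2.3 give 0.025 per comparison. Protocol 11.4.2.1 and the synopsis give 2.5% with a 97.5% interval.
- Protocol 11.5.1: "the significance level will be 0.025 for each comparison between the alirocumab group and placebo group".

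SAP 1.5 and 1.6, where statistical modifications would be declared, both say not applicable.

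**The concern.** The two sentences in SAP 2.4.4.1.1 govern the same test. They share the model, the Week 12 least-squares means and the placebo comparator, and the hypotheses between them define the active-arm mean for each alirocumab group. They cannot both be the decision rule.

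The second sentence also disagrees with itself, because a 97.5% interval excludes zero exactly when the two-sided p-value is below 0.025. Under it, a p-value between 0.025 and 0.05 would be declared significant while the reported interval covered zero.

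Two things are at stake. The overall 0.05 promised in SAP 1.3 and 2.4.4.3 would not hold if both contrasts were tested at 0.05. And two written thresholds for one primary test leave room for a choice after unblinding, which pre-specification is meant to remove.

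**Working it through.** **1. Which level does the sample size use?** Inputs from SAP 1.3 and Protocol 11.1: difference 30, common SD 25, power 90%, two-sided 0.025, 19 per arm. For a two-sample t-test the noncentrality is 30 / (25 × √(2/n)) on 2n − 2 degrees of freedom.

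| Two-sided level | n = 16 | n = 18 | n = 19 | Smallest n for 90% |
|---|---|---|---|---|
| 0.025 | 0.843 | 0.889 | 0.908 | 19 |
| 0.05 | 0.907 | 0.938 | 0.949 | 16 |

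The plan's 19 per arm is reproduced at 0.025. At 0.05 it would have been 16. (The normal approximation gives 18 and 15.)

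**2. Familywise error for the two primary contrasts.** With 1:1:1 allocation and a shared placebo arm, the two test statistics have correlation 0.5. The error is 1 − P(|Z1| < c, |Z2| < c), with c = 2.241 at level 0.025 and c = 1.960 at level 0.05. For independent tests it is 1 − (1 − α)².

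| Level per contrast | Bonferroni bound | Shared placebo | Independent |
|---|---|---|---|
| 0.025 | 2 × 0.025 = 0.05 | 0.0465 | 1 − 0.975² = 0.0494 |
| 0.05 | 2 × 0.05 = 0.10 | 0.0907 | 1 − 0.95² = 0.0975 |

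Only 0.025 per contrast meets the stated overall 0.05.

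**3. Where do the two thresholds disagree?** Inputs: 53 per arm, SD 25, no covariate adjustment, no missing data.

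- SE = 25 × √(2/53) = 4.856, with 2 × 53 − 2 = 104 degrees of freedom.
- Critical difference at 0.05: 9.63 points.
- Critical difference at 0.025: 11.05 points.
- Example: p = 0.03 corresponds to a difference of 10.7 points, with a 97.5% interval of −0.4 to 21.7. This is significant under the second sentence and not under the first.

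**4. How likely is that window?** With a true difference of 30 points, power is 0.99994 at 0.025 and 0.99998 at 0.05. The probability of a p-value between the two levels is 4.1 × 10⁻⁵, about 0.004%.

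**5. Is there another reading of the 0.05?**

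- As the overall level: no. The sentence applies it to the contrast and pairs it with a 97.5% interval.
- As the Q4W versus Q2W comparison: no. That has its own sentence, with a 95% interval, and Protocol 11.4.2.2 calls it descriptive.
- As a pooled alirocumab comparison: no. None is defined; SAP 1.3 plans two pairwise comparisons.
- As a deliberate change: no. SAP 1.5 and 1.6 declare none.

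**The case against.** The best reply is that the intended level is not in doubt. SAP 2.4.4.3, the dedicated multiplicity section, fixes the primary tests themselves at 0.025, not only the gate to the key secondaries. The earlier sentence in 2.4.4.1.1, the 97.5% interval in the faulty sentence, the sample size and the protocol all agree with it. On this view 0.05 is the overall level put in the wrong slot, and the familywise figures above describe a procedure that the plan as a whole never adopts.

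The practical effect is also tiny. Protocol section 4 reports earlier differences from placebo well above 30 points: −44.9% at Week 12 for 150 mg Q4W in a phase 3 study, and −57.2% to −69.1% for 150 mg Q2W in phase 2. At 44.9 points, with SD 25 and 53 per arm, the chance of landing between the thresholds is about 2.5 × 10⁻¹².

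Most of this stands. It is a drafting error, the key secondary hierarchy is protected by its explicit 2.5% condition, and the inflated error rate is conditional on someone following the faulty sentence. The comparison is also limited to the text available: the SAP contents list an Appendix B summarising the statistical analyses, which could not be checked. None of this makes the sentence correct. An analyst should not have to infer the confirmatory threshold by weighing other sections against the one that specifies the test.

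**Conclusion.** The concern holds. The 0.05 level in SAP 2.4.4.1.1 is wrong as written: it contradicts the same section, the interval in its own sentence, and every other per-comparison level in the available text of both documents.

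Used for both arms, it would raise the familywise error to 9.1% with the shared placebo arm, or 9.75% if the contrasts were independent. The corresponding figures at 0.025 are 4.6% and 4.9%.

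The practical risk to the primary conclusion is very low, about 0.004% under the planned 30-point difference. That figure assumes 53 evaluable patients per arm, SD 25, and an unadjusted t-test standing in for the MMRM. The reason to correct it is that a primary test needs one unambiguous decision rule, not that the result is expected to depend on it.

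**What to change.** In SAP 2.4.4.1.1, revise the sentence after the hypotheses so that each alirocumab group is compared with placebo by a contrast at the two-sided 0.025 level, and keep the 97.5% interval. Make the change before the first database lock, and check that any alpha stated in SAP Appendix B agrees. The cost is one sentence. Design, sample size, model and testing hierarchy are unchanged.
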